### **Methods of Statistical Analysis**

According to the principle of intention-to-treat (ITT), our data will contain all subjects enrolled. Efficacy and safety measures will be analyzed in accordance with protocol strictly, thus, only subjects who completed the entire trial and followed the protocol requirements should be analyzed. Quantitative and qualitative variables are described statistically with  $X \pm SD$  and count numbers, separately. Quantitative variables will be analyzed by one-way ANOVA (SNK method) in statistic, a normal data distribution needed before performance. Qualitative variables will be analyzed using either  $\chi^2$  test or Fisher' s exact test. All statistical tests are two-sided, and P value  $< 0.05$  will be considered to be statistically significant. Statistical analysis will be performed using SPSS 17.0 software for application.

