### **Study subject**

The study subject is elder inpatient who will be undergoing elective total knee arthroplasty under epidural anesthesia, age from 65 to 85 years old, ASA physical status of I-III, and agree to the informed consent form. The exclusion criteria are the subject (1) refuse to participate in the study; (2) already participate in other clinical studies; (3) is not available due to severe physical status, like ASA classification of IV; (4) required emergency patient; (5) is not suitable to TEAS requirement, e.g. pace maker or metal implant; (6) has deficiency in cognition and literacy and medical history of mental disorder, deep venous thrombosis, or history of drug abuse and acupuncture. Subject should be removed if he/she: (1) switch to general anesthesia; (2) refuses to continuous TEAS administration without any excuse; (3) gets serious adverse reactions in treatment period (e.g. cardiac arrest, comatose); (4) can't accomplish the follow-up visit; (5) acupuncturist changed; (6) low compliance patient.

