### Sample Size Calculation

This trail contains two groups. A sample size estimation formula can be used to calculate the numbers of subjects in each group, base on two-groups, randomly, controlled design.

$$n = \frac{(Z_{1-\alpha} + Z_{1-\beta})^2 \cdot (\sigma_1^2 + \sigma_2^2)}{\delta^2}$$

where  $n$ ,  $\sigma$ ,  $\delta$  represent the sample size in each group, standard deviation, mean difference of two groups, respectively. In a condition of  $\alpha = 0.05$ ,  $\beta = 0.1$  with a two sided test, we obtain  $Z_{1-\alpha} = 1.96$  and  $Z_{1-\beta} = 1.282$ . According to previous data by Bai et al, the primary outcome of QoR-40

in the article is  $176.9 \pm 11.1$  vs.  $164.3 \pm 13.7$  as compare experimental group to control group ( $p = 0.006$ ), the sample size for each group was 21 cases and the final sample size estimated in each group was 26 cases with adding a 20% dropout rate. Totally 54 subjects are needed.

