### **Control group**

The subject in group C will obtain a sham stimulation, which means the medical electrode adheres to the same acupuncture points as experimental group without actual electrical stimulus (or

attached to an inactive electrical stimulator). All other procedures else are same as the participant in group E except for stimulation intensity.

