### **Study protocol**

All participants will fill a demographic information sheet (including age, gender, height, weight, ASA classification status, education level, income, previous anesthesia experience/complications, medical history, anxiety and depression, preoperative examination and based line functional ability). The first assessment of patient status will take place at 1 day before surgery (baseline), and repeat at 1st day, 3rd day, 7th day after surgery.

**Safety Assessment:** We will define an adverse event as an event if more than three subjects suffer a same symptom, such as local skin rash, dizziness, and low blood sugar during the treatment-evaluation period. These events will be statistically analyzed, and treatment safety is evaluated in accordance with the research protocol. If serious adverse events occur, we will report it immediately and take actions accordingly.

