### **Statistical Analysis**

1. Content of statistical analysis: a. Dropout sample: the accuracy numbers lost and dropout rate of subjects are described, and reasons for the dropout is given. b. Balance comparison: The

comparability of subjects in two groups are compared via the baseline information assessing. c. Efficacy analysis: we will treat the QoR-40 as the primary outcome to evaluate the efficacy of TEAS treatment in improving the postoperative recovery after total knee arthroplastic, a mean and deviation as the expression of primary outcome and compared between groups using one-way ANOVA (SNK method), however, before statistic performed, a test of normal distribution of data should be used to determine whether the data are suitable for analysis using the one-way ANOVA. Additional four composite outcome measures (incidence of any postoperative complication, length of hospital stay, level of stress response, level of inflammatory response) are also used as secondary outcomes to determine the efficacy of

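### The plan names intention-to-treat but restricts efficacy and safety analysis to protocol-following completers, so the only analysis it specifies is per-protocol, with bias of unknown size and direction.

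*Combined protocol and SAP*

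**What the plan says.** Methods of Statistical Analysis opens with "According to the principle of intention-to-treat (ITT), our data will contain all subjects enrolled". The following sentence covers efficacy and safety measures and ends: "only subjects who completed the entire trial and followed the protocol requirements should be analyzed".

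Study subject says who is removed. The reasons are conversion to general anaesthesia, refusal of stimulation, serious reactions ("gets serious adverse reactions in treatment period (e.g. cardiac arrest, comatose"), incomplete follow-up, and finally "5) acupuncturist changed; (6) low compliance patient". Low compliance is not defined.

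On safety, the Study protocol section says of adverse events: "These events will be statistically analyzed, and treatment safety is evaluated in accordance with the research protocol". On losses, Statistical Analysis promises only description: "the accuracy numbers lost and dropout rate of subjects are described, and reasons for the dropout is given". Sample Size Calculation makes a numerical allowance: "the final sample size estimated in each group was 26 cases with adding a 20% dropout rate".

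**The concern.** The two sentences cannot both govern the same analysis. The restrictive one names efficacy, so it reaches the primary outcome, QoR-40. The text assigns no efficacy analysis to the ITT set and does not say which set is primary.

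Every listed removal reason can arise after randomisation, and several could depend on the arm. The experimental (E) and placebo (P) groups are stimulated at each patient's maximal tolerance. The control group (C) has electrodes at the "same acupuncture points as experimental group without actual electrical stimulus". Refusal or poor compliance could therefore be commoner in E and P. Incomplete follow-up could instead be commoner in C if recovery is worse there, which would pull the comparison towards no effect. E versus P is less exposed, since both are set to maximal tolerance.

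The safety problem does not depend on rates. Serious reactions are a reason for removal, and safety is then analysed only in those who remain. A reader would take the efficacy result as ITT and the safety table as complete, and neither would be so.

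**Working it through.** **Planned figure.** From Sample Size Calculation: means 176.9 and 164.3 (difference 12.6), SDs 11.1 and 13.7, two-sided alpha 0.05, beta 0.1.

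- n = (1.96 + 1.282)² × (11.1² + 13.7²) / 12.6² = 10.51 × 310.9 / 158.76 = 20.6, rounded up to 21. This agrees with the plan.
- 21 × 1.2 = 25.2, rounded up to 26, also as stated. Dividing by 0.8 instead gives 26.25, that is 27.
- Average SD = √(310.9 / 2) = 12.47.

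If 20% of 26 are lost, about 21 per group are analysed. Normal-approximation power at 12.6 points is 90.6% with 21 and 95.4% with 26. The allowance therefore protects precision. It does nothing about selection.

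**Size of the selection bias.** No removal rate by arm is given, so this is an illustration. Let removed patients score g points below completers in every arm. The completer mean exceeds the all-randomised mean by (share removed × g), so

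shift in E − C = (share removed in E − share removed in C) × g.

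Type I error is from simulated two-group t-tests on retained patients, with 26 randomised per arm and no true difference between the all-randomised means.

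| Removed, E v C | Shift, g = 1 SD (12.47) | Type I error | Shift, g = 0.5 SD | Type I error |
|---|---|---|---|---|
| 20% v 20% | 0 | about 5% | 0 | about 5% |
| 20% v 10% | 0.10 × 12.47 = +1.25 | 6.3% | +0.6 | 5.3% |
| 20% v 0% | 0.20 × 12.47 = +2.49 | 10.1% | +1.25 | 6.3% |

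With g at 0.25 SD, 20% v 0% gives +0.6 points and 5.3%. If C loses more patients than E, the signs reverse. Against the planned 12.6 points, 1.25 is 10% and 2.49 is 20%. With g from 5 to 15 points and removal from 0 to 30% per arm, the shift runs from −4.5 to +4.5 points.

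**Hand check of the 20% v 0% case, 1 SD.** SE = 12.47 × √(1/21 + 1/26) = 3.66. Shift/SE = 2.49/3.66 = 0.68. Two-sided error ≈ P(Z > 1.96 − 0.68) + P(Z < −1.96 − 0.68) = 0.100 + 0.004 = 10.4%, in line with the simulation.

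**Power if non-adherers are kept.** Suppose 20% of E gain nothing. The expected difference is 0.8 × 12.6 = 10.08.

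- At 26 per group: 10.08 / (12.47 × √(2/26)) − 1.96 = 0.955, power 83% (t-test 82%).
- At 27 per group: 84% (t-test 83%).
- Mixing responders and non-responders raises the SD in E to √(12.47² + 0.8 × 0.2 × 12.6²) = 13.45. T-test power is then 78% at 26 and 80% at 27.
- If the stated total of 54 is split over three arms, 18 each: 68% (t-test 65%; 62% with the larger SD in E).

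**The case against.** The kindest reading is that two analysis sets were run together in one paragraph: ITT for one purpose, completers for another. In addition, the Statistical Analysis section breaks off mid-sentence in the available copy, so something relevant may be missing there. Both points limit what can be said about absence. Neither removes the explicit completer rule, which is the only rule tied to an analysis, and neither settles which set is primary.

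The magnitude can also be challenged. A 1 SD deficit is nearly the whole planned effect, and 20% v 0% is extreme. Stimulation is confined to the surgical day, its intensity is set by the patient's own tolerance, and outcomes end at day 7. Only the stimulation operator is said to know the allocation. A change of acupuncturist or of anaesthetic has no evident link to arm. The type I figures use a two-group t-test, whereas the plan specifies ANOVA with SNK. These points stand as limits on size, and the 0.5 and 0.25 SD results show how much smaller the effect could be. They do not make the rule sound.

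Serious events are not hidden: they are to be reported at once, complications are recorded, and dropout reasons are given. What is lost is their place in the between-group safety analysis.

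On cost, power with only 21 observed per group at 10.08 points is about 72–75%. That figure largely counts the same patients twice, since the non-adherers are mostly the dropouts now being retained. It becomes relevant only if scores are lost in addition. The figures at 18 per arm mainly reflect a separate problem: the sample size is for two groups while three are randomised. Before any dilution, 18 per arm gives about 84–86%.

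**Conclusion.** The point holds and must be fixed. Taken literally, the plan yields a per-protocol primary analysis described as ITT, and a safety comparison from which patients with serious reactions can drop out. This conclusion rests on the text alone.

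The size of the efficacy bias rests on assumption. It is about zero if removal is equal and by the same mechanism in each arm. Under a 1 SD deficit it is 1.25 to 2.5 points for 20% v 10% and 20% v 0% removal, with type I error of about 6% and 10%. Under smaller deficits it is less. The sign depends on which arm loses more patients. The undefined compliance criterion adds the risk that exclusions are settled after data have been seen.

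**What to change.** Reconcile Study subject with Methods of Statistical Analysis as follows.

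- **Primary set:** all randomised patients in their assigned group. State that the removal events are not grounds for exclusion from analysis. Rules for stopping treatment remain with the investigators.
- **Outcome collection:** continue after such events where possible.
- **Missing QoR-40 scores:** name one method, such as a mixed model for repeated measures or multiple imputation, and add a missing-not-at-random sensitivity analysis (for example a delta adjustment by arm). Say separately how patients unable to complete the questionnaire are handled, because a model would otherwise assign them hypothetical scores.
- **Safety set:** everyone who had electrodes applied.
- **Completer analysis:** sensitivity only, with low compliance defined before unblinding.

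The cost is wording in two sections plus follow-up that may fall after discharge by day 7. Power falls if non-adherers gain nothing: with 20% of E unaffected, it is about 78–84% at 26–27 per group, depending on the SD and approximation used. Any shortfall from splitting 54 patients over three arms should be dealt with in the sample size section.

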### **Outcome Measures**

Primary outcome measure: The primary outcome is the Quality of Recovery-40 questionnaire (QoR-40). It was specifically designed to evaluate quality of recovery in subject after surgery with including five aspects: emotional state, physical comfort, psychological support, physical independence and pain. There are 40 items in total, each adding 1-5 points to the score. Thus, the highest possible score is 200 points; higher scores indicate better quality of recovery. The QoR-40 will be evaluated at preoperative day 1 and postoperative day 1, 3, 7, respectively.

Secondary outcome measures: a. Incidence of postoperative complications: we will assess incidence of postoperative complications when initially find by participant or accompanying family members and diagnosed through examination or scale. Any complication after surgery will be recorded and filled in the case report form. When subject send back to ward, we will require the accompanying family members to record any complaint from subject. Assessment of incidence of postoperative complications will be going on three times and occur at postoperative day 1, 3, 7, respectively. b. The length of hospital stay (LOH): The LOH = the day of patient discharge from hospital – the day of patient admit to hospital, which is calculated base on the Hospital Information System. c. Level of stress response: The Adrenocorticotropic Hormone (ACTH), Cortisol (COR) are chosen to address the level of perioperative stress response. Blood sample taken intravenously and collected at the time of 1 day before surgery (baseline) and 1st day, 3rd day after surgery, respectively. d. Level of inflammatory response: In clinic, the C Reactive Protein and Neutrophil-lymphocyte ratio are well-known to represent the level of perioperative inflammatory response [27, 28]. Blood sample taken intravenously and collected at the time of 1 day before surgery (baseline) and 1st day, 3rd day after surgery, respectively.

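### ANOVA is conditional on normality for the primary and all quantitative secondary outcomes, with no other method named, so a failed check leaves the analysis to be chosen after the data are seen

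*Combined protocol and SAP*

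**What the plan says.** Statistical Analysis, on the primary outcome QoR-40: "a test of normal distribution of data should be used to determine whether the data are suitable for analysis using the one-way ANOVA".

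Methods of Statistical Analysis applies one-way ANOVA with SNK comparisons to all quantitative variables, on the same condition: "a normal data distribution needed before performance". The summary is mean and SD throughout. The only other tests named are chi-square and Fisher's exact, and these are reserved for qualitative variables.

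Outcome Measures shows what falls under the quantitative rule besides QoR-40: length of stay, ACTH and cortisol, and CRP and the neutrophil-lymphocyte ratio (NLR). For the four blood markers a preoperative value is taken: "Blood sample taken intravenously and collected at the time of 1 day before surgery (baseline) and 1st day, 3rd day after surgery, respectively". QoR-40 is also measured on preoperative day 1. The plan uses baseline information only to compare the groups for balance.

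The plan does not name the normality test or its level. It also does not say whether the test applies to each arm, to residuals or to each visit.

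**The concern.** The rule has a gate with one exit. If the check passes, ANOVA is run; if it fails, the plan is silent. Someone must then choose among a rank test, a transformation or ANOVA regardless, with the data in hand. Those choices can give different answers, and the reader of the final report could not tell whether the result influenced the method. This covers the primary outcome as well as the secondary ones.

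A second, smaller matter is efficiency. Concentrations, ratios and durations are positive and may be right-skewed, in which case a raw-scale comparison of means uses the data less well than a log-scale one. Baseline values are collected but do not enter the outcome analysis.

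**Working it through.** **Group size.** From Sample Size Calculation: means 176.9 and 164.3 (difference 12.6), SDs 11.1 and 13.7, Z values 1.96 and 1.282.

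n = (1.96 + 1.282)² × (11.1² + 13.7²) / 12.6² = 10.511 × 310.90 / 158.76 = 20.58, so 21 per group, as stated. Adding 20% gives 25.2, rounded up to the stated 26. The stated total of 54 over the three randomized groups is 54 / 3 = 18. I use 18 as the main case, with 21 and 26 for sensitivity.

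**How often the gate fails on normal data.** With a 5% test in each of three arms, the chance of at least one rejection is 1 - 0.95³ = 14.3%; simulation gives 13-15%. If QoR-40 is checked in each arm at each of its three postoperative visits, treating the nine checks as independent gives 1 - 0.95⁹ = 37%. A single test on pooled residuals would fail only about 5% of the time, so the unstated form of the test matters.

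**How often it fails on skewed data.** The lognormal shape and the log-SD are assumptions. Chance that all three arms pass Shapiro-Wilk at 18 per arm:

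| log-SD | all arms pass |
|---|---|
| 0.2 | 68% |
| 0.3 | 46% |
| 0.4 | 30% |
| 0.6 | 7% |
| 0.8 | 1% |

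Repeat simulations differ by up to about 3 points. With larger groups the gate fails more often: at 21 and 26 per group, failure is 38% and 43% at log-SD 0.2, 59% and 68% at 0.3, and 90% and 96% at 0.5.

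**Effect of choosing afterwards.** Three candidates: raw ANOVA, Kruskal-Wallis, and ANOVA on logs. Taking the smallest p-value gives a type I error of 6.3-7.5% at 21 per group over log-SD 0.3 to 1.0, and 6.6-8.5% at 26 per group (2,000 runs each, so a standard error of about 0.6 points). With one group shifted by 0.9 log-SD, an assumed effect, the three methods disagree on significance in 9% (log-SD 0.3) to 37% (log-SD 1.0) of trials at 21 per group.

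**Raw against log scale.** Two-group comparison of E with C, 18 per arm, same assumed effect:

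| log-SD | raw | log |
|---|---|---|
| 0.2 | 0.74 | 0.75 |
| 0.3 | 0.73 | 0.75 |
| 0.4 | 0.71-0.72 | 0.74-0.75 |
| 0.6 | 0.68 | 0.75 |
| 0.8 | 0.61-0.62 | 0.74-0.75 |

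The raw-scale type I error stays at 4-5% throughout. The plan's three-group F test at log-SD 0.3 gives 0.81 against 0.85 at 21 per group and 0.90 against 0.91 at 26.

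**Baseline adjustment.** On the log scale the noncentrality without baseline is 0.9 × √(18/2) = 2.70, power 0.75. With baseline correlation r it is 2.70 / √[(1 - r²)(1 + 1/32)], where the second factor allows for chance baseline imbalance among 36 patients:

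- r = 0.2: 2.71, power 0.75
- r = 0.3: 2.79, power 0.77
- r = 0.5: 3.07, power 0.85

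The gain is thus about 0 to 3 points at r = 0.2 to 0.3 and about 10 points at r = 0.5. The documents give no value of r.

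**The case against.** The sponsor could answer that this is one missing sentence: naming a rank test as the fallback would close the gap, and the log-scale and baseline-adjusted models are preferences. That is partly right. A pairwise Mann-Whitney test holds power of 0.71-0.72 at 18 per arm whatever the log-SD, within about 4 points of the log-scale t-test. But a named fallback would still let a preliminary test pick the method for each variable.

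The Statistical Analysis section breaks off mid-sentence in the text available, so a few words may be lost. Methods of Statistical Analysis, however, reads as complete and names no alternative.

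Four stronger readings are tempting and are not supported:

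- *The markers and length of stay are likely to fail the gate.* The documents give no distribution or SD for any of them. At log-SD 0.2 the gate passes in about two trials out of three.
- *Raw-scale ANOVA is invalid here.* Its error rate is kept even under marked skew.
- *The plan loses a lot of power by staying on the raw scale.* The large loss (0.61 against 0.74 at log-SD 0.8) arises where the gate passes in 1% of trials, so the plan itself would almost never run that analysis. Where the gate often passes (log-SD 0.2 to 0.4), the loss is about 1 to 3 points.
- *Most of the recoverable power is a consequence of the gate.* It comes from baseline adjustment, which is a separate matter and depends on an unknown correlation.

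**Conclusion.** The gap stands on the text alone: ANOVA is conditional on normality for the primary and every quantitative secondary outcome, and no other method is given. A failed check therefore means an analysis fixed only after the data are seen. How often that occurs depends on assumed skew and on how the check is applied, from about 5% (normal data, one test on residuals) to nearly always (log-SD 0.8, a test in each arm).

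The error inflation is modest, so the main harm is to the credibility of the analysis. Still, under the assumed effect the choice of method can decide whether a result counts as significant. Power is a supporting argument only. The point should be acted on, because the remedy is cheap and reaches the primary analysis, but it does not by itself undermine the trial.

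**What to change.** Delete the normality test as a condition for analysis and fix one method per outcome before unblinding:

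- **QoR-40:** linear model (ANCOVA) with group and preoperative day 1 QoR-40, used whatever a normality test shows, with a rank-based sensitivity analysis.
- **ACTH, cortisol, CRP, NLR:** ANCOVA on log values with log baseline as covariate, reported as geometric mean ratios with 95% confidence intervals.
- **Length of stay:** Kruskal-Wallis with pairwise Wilcoxon tests, reported as median and quartiles.

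The cost is SAP wording and minor programming, with no new data or visits. The small downside is that biomarker effects are reported as ratios, not as differences in the original units.
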